#### 11.5 Accrual number request

In order to accrue 24 subjects, we are requesting a total potential sample size of 30. This should account for patients who do not have enough seizures to qualify during baseline, as well as dropouts.

### 12. Human Subjects Protection

#### 12.1 Rationale for Subject Selection

Subjects will be selected based upon their meeting the study's eligibility criteria. Subjects will be admitted to the protocol without regard to 'race,' 'ethnicity,' gender, 'sexual orientation,' or other regardless of any non-medical personal characteristics.

#### 12.2 Justification for exclusion of children

PRX-00023 has not yet been given to children. Children are excluded from this study because safety has not been established in children and the efficacy for epilepsy is undetermined.

#### 12.3 Justification for exclusion of those over age 65

Patients over age 65 years old are excluded from this study because they are more likely than younger persons to have co-morbid conditions. Furthermore, previous clinical experience with PRX-00023 has been limited to those ages 18 – 65.

#### 12.4 Vulnerable subjects

Adults unable to give consent will not be included. If capacity is uncertain, NIH/CC/Bioethics/HSPU will be consulted. Pregnant women will be excluded, as PRX-00023 teratogenicity potential is unknown. Women who are able to become pregnant, and men will be required to use contraception throughout the protocol participation.

#### 12.5 Justification for use of placebo

Placebo-controlled studies are the only way to obtain reliable data on AED efficacy in a clinical trial in any epilepsy syndrome, including localization-related epilepsy. Seizures are largely self-reported, and placebo effects occur in all AED trials. Since this is an add-on study, patients will still be on their baseline AEDs during all treatment phases, and will not be exposed to any risk greater than their standard therapy while on placebo.

## 13. Potential Benefits

Patients may experience direct benefit while on the active medication due to:

Reduction of seizure frequency

Amelioration of depression and anxiety

Increased information on localization of their epileptic focus due to 18F-FCWAY PET

## 14. Summary/ classification of risk: for the study as a whole

This protocol is more than minimal risk.

The risks are reasonable in relation to anticipated benefit. Uncontrolled epilepsy is a serious illness with increased morbidity and mortality compared with the general population. Previous experience suggests that PRX-00023 has low toxicity. The radiation exposure from the PET scans to be performed is within the limits set by the NIH Radiation Safety Committee.

## 15. Consent documents and process

The study investigators authorized to obtain consent are indicated in section 12.6.

### 15.1 Non-English Speaking Participants

If a non-English speaking participant is unexpectedly eligible for enrollment, the CC standard short written consent form in the appropriate language and a written summary of what the

CNS IRB Protocol Template (rev.03-25-10)

Investigator will say to the participant will be used as part of an oral consent process. The IRB approved English written consent form will serve as the written summary if the short form process is used. The investigator will obtain an interpreter unless the investigator is fluent in the prospective participant's language. Preferably, the interpreter will be someone who is independent of the participant (i.e., not a family member). Interpreters will be found through the Department of Social Work. The interpreters will translate the current IRB-approved English version of the consent verbatim and facilitate discussion between the participant and investigator.

The written summary will be signed by the investigator obtaining consent and a witness to the oral presentation. The short written consent form will be signed by the participant and a witness who observed the presentation of information. The interpreter may sign the consent document as the witness and, in this case, will note "Interpreter" under the signature line. A copy of the signed form will be provided to the participant to take home.

The investigator obtaining consent will document the consent process in the participant's medical record, including the name of the interpreter. Further, all instances of use of the short form process will be reported to the IRB at the time of annual review.

## 16. Data and Safety monitoring

This protocol will utilize a Safety Monitoring Committee (SMC) and an Independent Medical Monitor (IMM) to review AEs and safety reports. The Safety Monitoring Committee will be composed of:

[name] MD. Board Certified in Neurology, Clinical Neurophysiology and Epilepsy, GW Medical Faculty Associates  
[name] NIH CC Pharmacy Pharm.D., BCPP, Clinical Pharmacy Specialist for NIMH  
[name] RN NIMH

The Safety Monitoring Committee (SMC) will meet in advance of enrolling the first subject to confirm the monitoring plan. The SMC will meet at intervals specified by the needs of the trial, via conference call, email, or web-meeting by a password protected phone line/secured email/web meeting. The SMC will meet at least annually while the study is open to enrollment or has participants in active follow-up, and more frequently if needed. Additional meetings may be scheduled when necessary for adequate monitoring. Safety data reports will be provided annually, including seizure frequency, toxicity reports, neuropsychological and mood testing, laboratory tests, EEG, ECG and clinical examination until the end of the trial. Results will be reported to the Principal Investigator, IRB, and NINDS Clinical Director. Data review will be blinded, and no interim analysis is planned.

[name], a Board-Certified neurologist with extensive clinical trial experience, will serve as Independent Medical Monitor (IMM). Patients will be monitored carefully by CES clinicians for any change in their clinical status, using reports of seizure frequency, adverse events and toxicity during patient/family communications, clinical exam, laboratory studies, and Hamilton Depression rating scale at clinic visits. The IMM will be notified regarding clinical issues that may arise during this trial. Intervention may be determined by the IMM and may include consultation, additional studies, or withdrawing the patient from the protocol.

### 16.1 Criteria for stopping the study

The study will be suspended if a serious adverse event, as determined by the SMC, occurs in a patient found to be on active treatment after breaking the blind occurs. The study will not be restarted until reviewed by the IRB. The study may be stopped if in the judgment of the SMC

there is evidence that Grade 3 toxicity on the NCI CTC, or an increase in seizures of more than three times baseline, has occurred in more than 50% of the patients.

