## 7.4 Study design

Following screening and a baseline phase (up to 6 weeks), patients will enter a treatment phase of 2 periods (Period 1 and Period 2) with a washout phase between periods 1 and 2. If patients have 4 seizures in less than six weeks during the baseline phase, they do not need to wait the entire 6-weeks to begin the treatment phase (Period 1) of the study. Each treatment period will last approximately 12-16 weeks. Following Period 1, there will be a wash-out of 4 – 6 weeks where no study medication will be taken. During each treatment period, there will be two Clinical Center visits. The first visit will entail clinical assessments and will occur 6-week +/- 2 weeks after starting the study drug and the second visit will entail clinical assessments and neuropsychological and mood assessment and will occur at the end of each maximum tolerated dose (MTD) treatment period. In addition, a follow-up visit will occur approximately one month following the end of the second treatment period that will include a physical examination and review of any adverse events. The total duration of the study is 42-46 weeks (+/- 4 weeks). Each clinic visit will last approximately one hour. The neuropsychological and mood evaluation at the end of each treatment period will last up to three hours.

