#### 7.52 Randomization to Active drug or Placebo

Subjects will be randomized at the end of baseline to either active drug or placebo using a 1:1 ratio per the randomization schedule. The randomization schedule will be generated, secured, distributed, and stored by the NIH Pharmacy. Patients may be outpatients or inpatients during titration depending on their geographical location, need for additional education on the titration process or if they are participating in concurrent studies with the Clinical Epilepsy Section. All patients will be given an exact written titration schedule to follow.

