#### 7.54 Washout Period

Following the completion of Period 1, there will be a washout period for approximately 4 to 6 weeks.

#### 7.55 Period 2

Following a washout period, patients will be crossed over to the alternative treatment arm, using the same titration schedule as for Period 1. Patients may be outpatients or inpatients during titration. Outpatients will be given an exact written titration schedule to follow. During Period 2, there will be regular communication with patients/families by phone, secure email and/or the clinical trial database. Communication with patients/families will occur approximately 6 times during treatment Period 2; about once every two weeks. Patients will keep seizure calendars. Patients will return to NIH 6 weeks +/- 2 weeks after the start of Period 2 and the tests listed in section 7.571 will be performed. At the end of the Maximum Tolerated Dose period, patients will again return to NIH for repeat of baseline testing (see section 7.572). Following testing, patients will be tapered off of Period 2 study drug..

The same titration, MTD treatment, and taper schedule as described in Period 1 will be used for Period 2. Period 2 will last approximately 12-16 weeks..

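### The more-than-50% stopping criterion in section 16.1 names no denominator or treatment period and is reviewed blinded, so patients not yet on active drug dilute it early in the trial

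*Combined protocol and SAP*

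**What the plan says.** Section 16.1 contains two criteria.

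- **Suspension.** The study is suspended for a serious adverse event, as determined by the SMC, that "occurs in a patient found to be on active treatment after breaking the blind occurs". It restarts only after IRB review.
- **Possible stopping.** "The study may be stopped if in the judgment of the SMC" there is evidence of Grade 3 toxicity, or "an increase in seizures of more than three times baseline, has occurred in more than 50% of the patients".

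The second criterion is discretionary. It names no treatment and no period, and it does not say whether the patients counted are those randomized, those exposed to active drug or those who completed.

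Section 16 adds: "Data review will be blinded, and no interim analysis is planned". The SMC is to meet at least annually, safety reports are annual, and results go to the Principal Investigator among others.

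On design, section 7.52 states: "Subjects will be randomized at the end of baseline to either active drug or placebo using a 1:1 ratio per the randomization schedule". The schedule is generated and held by the NIH Pharmacy, and no blocking is described. Section 7.4 states: "Each treatment period will last approximately 12-16 weeks", with a washout of 4 to 6 weeks between periods. In section 7.55, "patients will be crossed over to the alternative treatment arm".

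**The concern.** A percentage of all patients, read blinded, mixes patients who have taken active drug with patients who have taken only placebo. While many patients belong to the second group, even a high rate of harm on active drug gives a pooled percentage near or below one half. A blinded committee cannot tell a pooled 40% to 50% that comes almost wholly from active drug from one spread over both treatments.

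Section 8.1 says that PRX-00023 has not been given to patients with epilepsy. Early exposure is therefore when a cohort-level signal of Grade 3 toxicity or seizure worsening would be most useful, and it is also when this criterion is least able to give one.

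**Working it through.** The documents give no derivation or operating characteristics for the 50% threshold, so there is no stated figure to reproduce.

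**Inputs.** Threshold above 50% (16.1); 1:1 allocation (7.52); periods of 12–16 weeks and washout of 4–6 weeks (7.4); up to 30 patients and 20% dropout (11.4). Assumptions: all 30 randomized, exactly 15 per treatment, and independent patients. *Affected* means meeting either part of the criterion. The harm rates are illustrative.

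**1. Ceiling before any crossover.** If every active patient and no placebo patient is affected, the share is 15/30 = 50%. The same holds for 10/20 and 12/24. The criterion requires more than 50%, that is, at least 16 of 30.

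**2. Chance of exceeding the threshold before any crossover.** This is P(A + B ≥ 16), with A ~ Bin(15, a) for active and B ~ Bin(15, b) for placebo. The comparison counts active-exposed patients only: P(A ≥ 8).

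| a / b | Expected pooled share | Pooled, >50% | Active-exposed only, >50% |
|---|---|---|---|
| 80% / 5% | (12 + 0.75)/30 = 42.5% | 5.1% | 99.6% |
| 60% / 10% | (9 + 1.5)/30 = 35% | 1.2% | 78.7% |

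**3. After crossover begins.** A placebo-first patient starts active drug 12 + 4 = 16 to 16 + 6 = 22 weeks after starting Period 1. Read cumulatively, a crossed placebo-first patient is affected with probability 1 − (1 − a)(1 − b):

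- 80%/5%: 1 − 0.20 × 0.95 = 0.81
- 60%/10%: 1 − 0.40 × 0.90 = 0.64

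With k of the 15 placebo-first patients crossed, the count is Bin(15, a) + Bin(k, 0.81 or 0.64) + Bin(15 − k, b). Crossed patients are given their full-period risk, and active-first patients are counted for their active period only.

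| a / b | k = 0 | k = 5 | k = 15 |
|---|---|---|---|
| 80% / 5% | 5% | 72% | >99.9% |
| 60% / 10% | 1% | 17% | 88% |

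If active-first patients' later placebo-period events are also counted, the last entry becomes 92% and 80%/5% stays above 99.9%.

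**4. Partial exposure, no harm on placebo.** Suppose 20 of 30 patients have taken active drug (illustrative). The pooled criterion needs 16 affected out of 20 exposed; counting the exposed alone needs 11 of 20. At a 70% harm rate the chances are 24% and 95%; at 60% they are 5% and 76%.

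**5. Why the unnamed denominator matters.** Suppose 30 are randomized, 20% (6) leave before Period 2, and all 6 are placebo-first (the extreme case). Then 24 have taken active drug. At a 60% harm rate on active drug only, the chance of exceeding 50% is 33% if the denominator is the 30 randomized (16 needed) and 79% if it is the 24 exposed (13 needed).

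**The case against.** A reader might infer that harm caused by the drug can never exceed the threshold because half the patients are always on placebo. The documents do not support that. The trial is a crossover and the wording refers to what has occurred, so in Period 2 the patients then on placebo have already had active drug. Once all have crossed, the reachable share is 100%. In the extreme case of harm in every active and no placebo patient, one crossed patient is enough (16/30). At full crossover the pooled count performs well for high harm rates.

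The picture in step 2 is also a snapshot. It needs all 30 patients in Period 1 together, while a single centre with staggered entry will usually have some already crossed; no accrual rate is given. Exact balance is not stated either. If allocation were unblocked (assumption), the chance that more than half of 20 to 30 patients start on active drug is 0.41 to 0.43.

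A reader might also infer that no stopping criterion uses treatment identity, or that the SMC must wait for 50%. Neither is right. The suspension trigger acts on one serious event in a patient found to be on active drug, and the 50% criterion is left to the SMC's judgment. Patient-level protections (sections 7.573, 9.2 and 9.3) also operate throughout.

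These points limit the concern to early dilution and undefined terms. They do not remove it. The suspension trigger does not reach Grade 3 toxicity or seizure worsening that is not serious, patient-level handling does not describe the cohort, and discretion exercised on blinded pooled data lacks the information needed to attribute events.

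**Conclusion.** The criterion is underspecified and insensitive early on, but it is not impossible to meet. Before crossover and with exact balance, harm confined to active drug cannot exceed it, and with some harm on placebo the chance is about 5% (80%/5%) or 1% (60%/10%). Sensitivity recovers only as placebo-first patients themselves become exposed, each 16 to 22 weeks after starting: for 60%/10% it is still about 17% when a third of them have crossed.

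The sizes rest on 15 patients per treatment, independence, a cumulative reading and illustrative harm rates. The finding that the denominator, the period and the means of attribution are missing rests on none of these. A blinded review of a pooled count is coherent in itself. The difficulty is that section 16.1 relies on treatment identity for serious events, while section 16 withholds it for the events the percentage is meant to capture.

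**What to change.** Reconcile section 16 with section 16.1:

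- State which patients form the denominator (randomized, exposed to active drug, or completed) and which treatment period or periods the percentage counts.
- Have the pharmacy, which already holds the randomization schedule, tabulate Grade 3 toxicity and seizure increases above the stated multiple by treatment received at onset, for the SMC only. Investigators and patients stay blinded.
- Amend the blinded-review sentence in section 16 to allow this table, and say that it is a safety tabulation and not an interim efficacy analysis.

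The threshold and the decision to stop remain with the sponsor and the SMC; no replacement is proposed here.

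The cost is a wording amendment and one table per SMC review. The downside is that the SMC, or someone reporting to it, sees events by treatment. Because section 16 sends results to the Principal Investigator, the reports passed on must leave that table out.

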#### 17. Quality Assurance (QA)

##### a. Quality assurance monitor

The EMMES Corporation will perform protocol monitoring.

##### b. Quality assurance plan

QA review will be performed in accordance with the QA Monitoring/Auditing algorithm included in the NINDS Quality Assurance Protocol Audit Plan. The EMMES Corporation will perform protocol monitoring annually.

#### 18. Reporting of Unanticipated problems, adverse events and protocol deviations

The Principal Investigator is responsible for detecting, documenting, and reporting unanticipated problems, adverse events (AEs), including serious adverse events (SAEs), and deviations in accordance with NIH policy, IRB requirements, and federal regulations. Relatedness to the research of all serious adverse events will be determined by the PI in consultation with the CD.

Serious unanticipated problems, serious adverse events (including deaths) that are not unanticipated problems, and serious protocol deviations will be reported to the IRB and CD as soon as possible and in writing not more than 7 days after the PI first learns of the event, unless immediate reporting is waived for specific serious adverse events as noted below. Not serious unanticipated problems and not serious deviations will be reported to the IRB and CD as soon as possible and in writing not more than 14 days after the PI first learns of the event. Written reports will be submitted in PTMS.

All adverse events, deviations, and unanticipated problems will be summarized and reported at the time of Continuing Review.

The PI will immediately report SAEs to the Sponsor according to the requirements of 21 CFR 312.64(b) and as agreed upon with the sponsor. The PI will record nonserious AEs and report them to the Sponsor at the time of Continuing Review.

The following expected Serious Adverse Events will not be reported to the IRB immediately and within 7 days unless they occur at a rate or severity greater than expected:

Emergency Room visits and hospitalization related to seizure activity including seizure clusters, falls and injuries related to falls.

#### 19. Alternative therapies

There is no other way to receive PRX-00023 for epilepsy. Alternative possible approaches include additional current marketed AEDs, participation in other experimental drug trials, brain stimulation therapy, and surgical evaluation.

#### 20. Privacy

All research activities will be conducted in as private a setting as possible.

#### 21. Confidentiality

To ensure confidentiality, research records will be kept in locked files in the principal investigator's office, and clinical files will be kept in the NIH Medical Records department. Image files that include experimental details will be maintained in file systems accessible only to the physicians and other scientific and technical staff working with the principal investigator. Subjects will be identified by code on all case report forms.

## 22. Conflict of Interest

NIH guidelines on conflict of interest have been distributed to all investigators. No NIH investigators have reported a conflict-of-interest.

## 23. Technology Transfer

The study will be carried out under CRADA 2010-0071\_with Proximagen Limited, [name].

Proximagen is providing drug to NIH, and allowing NIH to cross-reference it's previous IND filings in filing the IND for the study. NIH will provide Proximagen the results of the study, with all data deidentified, as well as copies of annual and other reports to the FDA.

## 24. Research and Travel Compensation

No financial compensation will be provided to patients in the study.  
Reimbursement for travel expenses will be provided, based on NINDS and NIH guidelines.

## 26. Attachments/ Appendices

Study Calendar  
Eligibility checklist  
Case report / monitoring form  
NCI CTC  
Investigator's Brochure  
NIH 88-23a  
Jump Text Page

## 27. Consent forms

Adult subject
